document or script approved by the IRB. Prospective participant will not be enrolled when the person obtaining informed consent is unwilling to listen to or consider the information, even if the person providing informed consent agrees to be in the research. The informed consent process will continue throughout participation in the study, and consent will be informally verified on a continuing basis and recorded in the probation and clinical staff notes on an on-going basis. As a part of the on-going consent, significant new information will be given to the participant, and continuing consent will be documented as an addendum to probation and clinical staff notes with the PI being timely notified.

Screening and Enrollment

Screening will include review of inclusion and exclusion criteria such as age, custody status, length of stay, assent capacity, parental/guardian or LAR permission, language, and clinical stability and participation in the SLO County Juvenile Hall.

Study Visits

Because participants are housed in SLO County Juvenile Hall facility, all interactions will take place on-site. JIY will participate in baseline assessments at enrollment, followed by structured Heal intervention sessions for 8 weeks. Assessments (questionnaires, scales, journaling) will be repeated at 2-week intervals and at study completion. Session journals will be completed after each session inside the Healpod.

Standardized assessment will be completed as follows: Mini-IPIP-A (At the start), MAIA-Y (Baseline + midpoint + End), DERS-16 (Baseline + midpoint + End), TASC-R (Baseline + midpoint + End), PHQ-9 (every 2 weeks), GAD-7 (every 2 weeks) and PSS-4 (every 2 weeks) and KidCOPE (Baseline + midpoint + End). Each "visit" will consist of: (1) HealPod session (~5 minutes), (2) journaling (~5 minutes), and (3) therapy session with a therapist (~15 to 30 minutes).

Interventions

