Clinical stability: On-site clinical staff must confirm the juvenile is medically and psychiatrically stable enough to participate in the planned activities.
Willingness to participate: Youths must agree to comply with intervention procedures, including sitting in the Healpod, completing journaling or drawing after sessions, and completing study questionnaires.
- **Concurrent treatment:** Youth receiving standard counseling or prescribed psychotropic medication remain eligible for their normal ongoing treatment.

Vulnerable Populations

- **Inclusion of children:** Because participants are minors, parental/guardian or LAR consent is required in addition to participant assent. All study materials will be presented in age-appropriate language.
- **Inclusion of detained (prisoner) youth:** Individuals who are incarcerated or detained are eligible for this study. Given their custodial status, additional safeguards will be in place to minimize risk of coercion or undue influence:
- **Voluntariness:** Participation is voluntary. Refusal or withdrawal will not affect probation status, privileges, release dates, or case outcomes. “The minor advantages of participation (e.g., opportunity for relaxation, time for journaling, positive interaction with staff) are not of such magnitude that they would impair the youth’s ability to weigh risks and benefits or unduly influence their decision to participate.
- **Independent consent/assent:** Assent will be obtained by trained staff who are not in positions of custodial or disciplinary authority (e.g., not probation officers or detention guards). Youths will be given time to ask questions in private.
- **Age-appropriate materials:** Information sheets and assent scripts will be written in plain, adolescent-friendly language. Translations and verbal explanations will be provided as needed.
- **Parental/Gardian or LAR consent:** Written consent will be obtained from a parent, guardian, or LAR in addition to youth assent.
- **Confidentiality:** All data will be de-identified, stored securely on HIPAA-compliant servers, and not shared with probation or courts.

Regulatory and Ethical Safeguards

The study will adhere to ethical principles and comply with federal regulations governing research with vulnerable populations.

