- **Concurrent research participation:** Juveniles enrolled in another interventional research study that could confound outcomes of this trial
- **Consent/assent limitations**
 - Inability to provide verbal assent due to comprehension barriers
 - Lack of parental/guardian/LAR consent, where legally required
- **Research staff** will not personally use the device for research purposes. Their role is limited to facilitating device use for participants and monitoring protocol adherence.
- **Non-research use:** While the Healpod may be available for non-research use in other settings, this protocol strictly limits its use to the described research procedures. Any non-research use will be separated from this study, and no data will be collected from individuals outside of the study.

Vulnerable Population (Juvenile Prisoners)

- **Detained individuals not eligible:** Juveniles detained outside of SLO County Juvenile Hall will not be eligible for this trial.
- **Safeguards for detained participants:** For those eligible, participation must be voluntary. Refusal or withdrawal will not affect probation status, privileges, or case outcomes. Recruitment, assent and consent will be conducted by individuals not involved in disciplinary or release decisions.

Study Interventions/Activities

Description of Research Activities and Procedures

Screening and Enrollment: Eligible juveniles will be all those within the SLO County Juvenile Hall. Screening will confirm inclusion and exclusion criteria, including age, detention length, mental health/SUD diagnosis, language ability, and clinical stability. Written informed consent will be obtained from parent/guardian or LAR, and assent will be verbalized and explained to eligible juveniles before participation.

Baseline Assessment: At enrollment, participants will complete standardized measures, including the Mini-IPIP-A (at the start), MAIA-Y(Baseline + Midpoint + End), DERS-16(Baseline + Midpoint + End), TASC-R (Baseline + Midpoint + End), PHQ-9 (every 2

weeks), GAD-7 (every 2 weeks), PSS-4 (every 2 weeks), and KidCOPE (Baseline + Midpoint + End).

Intervention Delivery: Participants will complete up to 16 Heal sessions across 8 weeks (1 or 2 sessions per week). Each 5-minute session includes:

- **Sensory intervention:** 5 minutes of sound, music, and gentle vibrations
- **Journaling:** 5 minutes of expressive writing/journaling or drawing

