- Selection of subjects is fair, with recruitment facilitated by clinicians and probation officers based on clinical stability, not by staff preference.
- Any possible advantages of participation (~5 minute sessions, journaling or drawing, increased readiness for therapy) are modest and comparable to ordinary recreational or therapeutic activities within the facility. They are not of such a magnitude that they could impair participants’ ability to weigh risks against benefits.
- Pregnant individuals are excluded from participation, which provides additional protections for pregnant women. Given the absence of pregnancy-related data on vibro-acoustic and light-based interventions, the study adopts an exclusion.
- The risks involved in participation are commensurate with those that would be acceptable to non-detained adolescents participating in behavioral health research. The Heal intervention is non-invasive, brief, and similar in nature to standard wellness activities such as listening to music, mindfulness, or journaling and drawing. Sessions are overseen by clinical staff, and participants remain fully conscious and free to withdraw at any time. No risks unique to detention are introduced, and no greater risks are presented than would be expected in a comparable non-prisoner study population.
- The potential advantages of participating in the HealPod program are modest and comparable to those available through standard therapeutic services. They are not of such magnitude that they could impair a youth’s ability to weigh risks or make a voluntary decision to participate within the custodial environment.

- **Follow-up care:** Adequate provisions have been made for follow-up examination or care after participation ends, recognizing the varying lengths of individual sentences. Participation in the HealPod program does not require any medical follow-up. Youths will continue to receive standard clinical and therapeutic services provided regardless of whether they show any signs of emotional distress or not after participation, and their therapists will remain available for ongoing support. Participants will be informed during the consent/assent process that these follow-up provisions are in place and that their access to routine care is unaffected by study completion.

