Safety Monitoring Analysis

All AEs, SAEs, and Unanticipated Problems will be collected and documented. Because of the expected low event frequency, no inferential testing will be conducted for safety data. Any serious adverse events (SAEs) or unanticipated problems that arise will be reported.

Consent Process

Traditional Consent Process (Paper & Wet Ink)

- The person providing consent (parent/legal guardian/LAR) will be given as much time as they need to review study information and to make an informed decision.
- If more time is needed than the research timeline allows, the juvenile will not be enrolled.
- Probation/clinical staff at the SLO County Juvenile Hall will assess whether the parent/guardian/LAR or juvenile is under any pressure to decide quickly, and enrollment will not proceed if undue influence is suspected.
- No threat or adverse consequences will result if the parent/guardian/LAR declines participation.
- If the parent/guardian/LAR or juvenile indicates they do not wish to participate, the consent process will stop immediately.

- Probation/clinical staff will assess for coercion or undue influence by others and will not proceed if it is present.
- The consent process with the Junveniles will be conducted in age-appropriate basic level English.
- Presentation of the information will be adapted to the capacities of the parent/guardian/LAR and the juvenile in terms of intelligence, rationality, maturity, and language. The process will be culturally sensitive and be conducted in either basic level English or Spanish.
- All questions will be invited and answered.
- Probation/clinical staff will evaluate whether the parent/guardian/LAR and juvenile understand the study; if not, enrollment will not occur.
- No language will suggest waiving legal rights or releasing the sponsor/institution from liability.
- All the information in the consent document or script approved by the IRB will be communicated to the parent/guardian/LAR and the juvenile.
- The juvenile will not be enrolled if informed consent is not obtained.

Alternate Consent Process

Alternative approaches may be used if in-person paper consent is not feasible. Options include:

- **Asynchronous consent:** Parent/guardian/LAR may review consent forms online, discuss the study with research staff by phone or video, and then return signed forms via secure mail, email, or in person.

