- **Language and literacy accommodation:** For families with limited literacy, study staff will read forms aloud or provide simplified explanations in either basic level English or Spanish. Eligible juveniles will assent through both verbal affirmation and written signature.

Electronic Consent Process (compliant with part 11 for FDA-regulated studies)

Where in-person consent is not possible, electronic consent could be used that will meet 21 CFR Part 11.

- The probation/clinical staff will introduce the study through a secure electronic consent platform.
- Parent/guardian/LAR will review the materials independently and will have time to ask questions.
- Questions can be addressed through phone, video call, or secure platform messaging.
- After review and discussion, eligible juveniles and their parent/guardian/LAR will provide electronic signatures within the platform.

- The platform will meet 21 CFR Part 11 standards for identity verification, audit trails, secure storage, and authenticity of electronic records.

Waivers (Documentation Waivers, Consent Waivers, HIPAA Waivers)

Consent Waivers

A waiver of parental/guardian/LAR consent is not requested for this study, as participants are minors and juveniles. Written parental/legal guardian/LAR consent will be provided.

HIPAA Waivers

Recruitment will be conducted solely by San Luis Obispo County Juvenile Hall behavioral health staff. The research team will not access identifiable health information prior to consent. Therefore, a HIPAA waiver and HIPAA authorization are not required.

Privacy and Confidentiality

Protecting juvenile privacy and ensuring data confidentiality are paramount to the ethical conduct of this research. A robust data protection plan will be implemented to safeguard participant information throughout the study.

Data Minimization and Pseudonymization

Only information directly relevant to the study objectives will be collected. Identifiable data, such as names, booking numbers, probation ID, court case number, and medical record numbers will not be included in the research dataset. Each participant will be assigned a unique study ID. A secure linking log will be maintained locally at SLO County Juvenile Hall to connect study IDs with source records, available only to authorized site staff for audit, safety monitoring, or regulatory purposes. Research analyses will be conducted on pseudonymized datasets.

Data Security

A multi-layered data protection plan will be implemented:

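### The protocol gives probation officers a part in recruitment that its own independence rules exclude, and leaves open their part in the consent process

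*Protocol*

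**What the plan says.** Three places in the protocol keep custodial and release authority away from entry into the study:

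- Vulnerable Populations, on independent consent and assent: "Assent will be obtained by trained staff who are not in positions of custodial or disciplinary authority (e.g., not probation officers or detention guards".
- Vulnerable Population (Juvenile Prisoners), within the exclusion criteria: "Recruitment, assent and consent will be conducted by individuals not involved in disciplinary or release decisions".
- HIPAA Waivers: "Recruitment will be conducted solely by San Luis Obispo County Juvenile Hall behavioral health staff".

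The inclusion criterion on capacity to assent agrees with these and names clinical staff as the people who obtain assent.

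Other places bring probation staff in:

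- Subpart C: Prisoner Protections: "Selection of subjects is fair, with recruitment facilitated by clinicians and probation officers based on clinical stability, not by staff preference".
- Electronic Consent Process: "The probation/clinical staff will introduce the study through a secure electronic consent platform".
- Traditional Consent Process: "Probation/clinical staff will assess for coercion or undue influence by others and will not proceed if it is present" and "Probation/clinical staff will evaluate whether the parent/guardian/LAR and juvenile understand the study; if not, enrollment will not occur". A further item there has the same combined group judge whether the parent or juvenile is being pressed to decide quickly.
- Consenting, under Interactions with Participants: continuing consent is to be "recorded in the probation and clinical staff notes on an on-going basis".

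Finally, the Consent and Assent Process section promises, without qualification, that parole boards and probation staff will not be informed of a youth's participation.

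**The concern.** The participants are detained minors, and voluntariness is the first safeguard listed in the Subpart C section. Part of that safeguard is that whoever approaches the youth has no power over discipline or release. If one section gives probation officers a part in recruitment and another forbids it, staff can follow the section in front of them and still depart from the protocol.

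What is at stake is whether assent is free, and whether the assurance given to youths and guardians about what probation staff will know is accurate.

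**Working it through.** No arithmetic applies; the protocol gives no figure on this point. The check sets its statements side by side.

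**Step 1: do probation officers belong to the excluded group?** Yes, on the protocol's own text. The Vulnerable Populations section uses them as its example of custodial or disciplinary authority. The item on parole board protections under Subpart C lists them with parole boards among the authorities that decide parole status, probation terms and release dates. The rule for juvenile prisoners, which excludes those involved in disciplinary or release decisions, therefore covers them.

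**Step 2: recruitment.**

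| Section | Who recruits | Room for probation officers? |
|---|---|---|
| HIPAA Waivers | Behavioral health staff, exclusively | No |
| Vulnerable Population (Juvenile Prisoners) | Persons outside disciplinary and release decisions | No, by step 1 |
| Subpart C: Prisoner Protections | Clinicians and probation officers, as facilitators | Yes, explicitly |

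The third row contradicts the first two.

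**Step 3: assent and consent.**

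| Function | Section | Assigned to |
|---|---|---|
| Introducing the study | Electronic Consent Process only | Probation/clinical staff |
| Check for pressure to decide quickly | Traditional Consent Process | Probation/clinical staff |
| Check for coercion by others | Traditional Consent Process | Probation/clinical staff |
| Check of understanding | Traditional Consent Process | Probation/clinical staff |

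The slash allows either group. Clinical staff alone could perform all four functions and satisfy every section. Equally, nothing in these sections stops a probation officer from performing them, which would go against the independence rules. This is a permission that needs closing, and is weaker than the conflict in step 2.

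**Step 4: the promise about information.** Someone who helps recruit a youth, or checks that youth's understanding, knows of the participation. So does anyone who keeps the notes in which continuing consent is recorded. The recruitment role and the notes are stated outright; the consent checks are optional. Each is incompatible with the promise in the Consent and Assent Process section. The record in probation notes conflicts with this promise, and not with the three independence rules, which say nothing about record-keeping.

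**Step 5: other probation roles that touch the promise.** Key Design Features lets probation staff administer assessments. Study Procedures and Timeline lets them conduct the exit interview. The Introduction relies on their supervision of Healpod sessions. Correcting the recruitment and consent text alone would not make the promise literally true.

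**The case against.** The strongest reply is that the sections can be read together. To facilitate is not to conduct: probation officers might only supply the records used to judge eligibility, and the inclusion criteria do draw on probation records. The combined staff label can be met by clinical staff, who are already named as obtaining assent. The protocol also says repeatedly that participation has no effect on probation status or privileges.

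Much of this stands for the consent sections, and for that reason they are described here as permissive. It does not rescue the recruitment sentence. A rule that behavioral health staff recruit exclusively leaves no recruiting role for probation officers, however light, and the sentence is the protocol's own Subpart C argument for fair selection.

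A reader might go further in four ways that the document does not support:

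- *That probation staff's own influence is never checked.* The item on pressure to decide quickly stops enrollment on any suspicion of undue influence and is not limited to influence from others. Youths also get time for private questions, and willingness to continue is checked every two weeks. What remains fair is to ask who runs the checks.
- *That probation staff introduce the study to every youth.* That wording appears only in the electronic route, which is a fallback when in-person consent is not possible.
- *That the special exclusion for coercion is triggered.* Its example is enrollment tied to privileges or probation decisions. A recruiter's job title is not such a tie.
- *That self-reported improvement is inflated.* A wish to please that is present at both baseline and Week 8 would partly cancel in within-person change, and favorable baseline answers would leave less room to improve. Neither direction nor size is established.

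**Conclusion.** The point holds in this form. The Subpart C sentence on recruitment contradicts the HIPAA Waivers section and the rule for juvenile prisoners. The consent sections allow probation staff into steps that the independence rules are meant to keep from them. Recruitment by probation officers, any consent role for them, and the probation notes conflict with the promise that probation staff will not learn of participation.

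The size cannot be put as a number. The recruitment sentence is general, so it reaches every youth recruited: up to 8 according to Key Design Features, or no more than 18 according to the Statistical Analysis section. How many would actually be approached by a probation officer is not known.

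The conclusion assumes only that the protocol's own descriptions of probation officers' authority are correct. The consequence is for voluntariness of assent and the accuracy of what families are told; the document gives no ground for extending it to the outcome scales. The recruitment contradiction should be corrected before youths are approached.

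**What to change.** 1. Subpart C: Prisoner Protections: delete *and probation officers* from the sentence on recruitment.
2. Traditional and Electronic Consent Process: wherever the combined probation/clinical label appears, name behavioral-health clinical staff who have no custodial, disciplinary or release authority.
3. Traditional Consent Process: delete *by others* from the coercion check, so that it plainly covers facility staff.
4. Consenting: record continuing consent in the clinical notes only.
5. Reconcile probation staff's part in assessments (Key Design Features), exit interviews (Study Procedures and Timeline) and session supervision (Introduction) with the promise in the Consent and Assent Process section, by changing either the roles or the promise.

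The three independence rules can then stand as written. This is a wording amendment that applies rules the sponsor has already stated. Its cost is that consent conversations, and the checks of understanding, pressure and coercion, must fit clinical staff schedules. The protocol already gives clinical or behavioral health staff the recruitment and assent roles, but it does not show that they now carry out those checks alone, so their availability should be confirmed.
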